Activity	Screen	Pre-op (baseline)	Pre-op after epidural, before bolus	Pre-op after epidural, after bolus/before anesthesia	Intra-op	Post-op Recovery (PACU)	1 hour post-op	Transfer to floor	POD 1	POD 2	POD 3
Informed consent	Х										
Inclusion / Exclusion Criteria	Х										
Medical History	Х										
Randomization		Х									
IV Placement		Х									
Primary measurements(SBP,DBP,MAP, HR,SaO2,RR,Pain score?) every 3-5 min		х	х	х	х						
Epidural Placement		Х									
Administration of Pre-op sedation			х								
Prep and supply of test drug			Х								
Infusion of Study drug if randomized for test group				х							
Infusion of Ropivacaine				х							
Primary measurements every 15 min						х	х				
(Secondary measurements) Sensory block assessment (1 hour post-op and every 6 hours for the subsequent 72 hours						x	х		x	x	x
Intra-op surgical records					Х						
Anesthesia Pain Service records			х	х	х	х	х	х	х	х	х
Pain Scores DVPRS Score							Х		Х	Х	Х
Record 24 hour I/Os						Х			Х	Х	Х
Pain management and "Rescue Drug" administration as needed							х	х	х	х	х
Record opioid usage						Х	Х	Х	Х	Х	Х
All SOC points and monitors: EKG, non-invasive BP; ETCO2; pulse ox; arterial line with Flow Track (if indicated); peripheral or central venous line; induction and mode of anesthesia.		x									
Physical therapy rehabilitation records (Time and distance of ambulation)									x	х	х

Patients will be approached about their willingness to participate in this study either in a pre-operative surgical or anesthetic clinic visit or in the pre-operative area on the day of surgery. Consent will be obtained by a member of the research team. The patient will be given time to read the consent, have all study related questions answered, and discuss the study with their family, if desired. A copy of the signed consent will be placed in the patient's physical chart, and a research progress note documenting study enrollment will be made in the patient's electronic medical record.

Inclusion criteria:

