Patients will receive a bolus of 500 mL of 5% Albumin intravenous infusion as per the usual routine practice of the APS before the main bolus dose is injected. A preoperative level of block will be established that is appropriate for the surgery by injecting an appropriate volume of ropivacaine 0.5% or lidocaine 2% w/ epinephrine 1:200,000 (5–10 mL) into the epidural space as per the usual practice of the APS. This will be done after the routine test dosing with 3 mL of 2% lidocaine and 1:200,000 epinephrine, confirmed that intrathecal and intravascular markers are negative. If an insensate-to-cold area in the appropriate dermatomes cannot be established within 10 minutes following a 5 to 10 mL (maximum 10 mL) injection of ropivacaine 0.5%, the epidural catheter will be removed and replaced. If this process is repeated and there was still no level, it will be annotated and the patient will be removed from the study, labeled as a primary block failure, and treated appropriately by the attending anesthesiologist by either repeating the epidural block placement a third time or using other appropriate perioperative analgesia.

Research-Related Procedures - Preoperative Period:

Once consent is obtained, patients will be randomly allocated by computergenerated randomization to one of four groups. This will be a quintuple blinded prospective study. The anesthesiologist managing the intraoperative anesthesia, the anesthesiologists (APS) placing the blocks and following the patients on the floors, the research nurse taking the measurement, the surgeons, nor the patients will be aware of what combination of drugs are used for the epidural block infusion.

The three groups will consist of:

- 1. Group A (Ropivacaine 0.2% infusion; Control group)
- 2. Group B (Ropivacaine 0.2% + 2 mcg/mL epinephrine)

3. Group C (Ropivacaine 0.2% + 5 mcg/mL epinephrine)

The pharmacists will make up and supply test drugs for groups A, B and C and provide them labeled to the block area drug dispenser as "A, B, or C test solutions" without specifically identifying the content.

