Primary measurements:

Include the average invasively or non-invasively measured SBP, diastolic blood pressure (DBP), MAP, arterial blood oxygen saturation (SaO2), heart rate, respiratory rate, and pain by the visual analog pain score (VAS) on the "Defense and Veterans Pain Rating Scale" (DVPRS) measured over the following set periods:

Preoperative period

Primary measurements every 3 to 5 minutes and at indicated time points:

- I. Before the bolus epidural is injected.
- II. After the epidural bolus is injected but before anesthesia is induced.

Intraoperative period

Primary measurements every 3 to 5 minutes

Postoperative period

I. Primary measurements in the recovery room (if appropriate) every 15 minutes

II. Primary measurements following transfer to the floor every 4-6 hours if within normal limits, but every hour if needed for closer observation in case of possible abnormality for as long as the epidural analgesic blocks are continued, but at least every 8 hours after discharge from the PACU.

Secondary measurements:

[figure not shown]
- III. Spread of block per spinal root segment as tested by sensitivity to cold recorded every hour postoperatively and every 8 hours for the subsequent 72 hours after discharge from the PACU.
- IV. Ambulation on the first day after surgery (POD 1), POD 2 and 3, will be recorded per physical therapy protocol and distance ambulated per 24hour period will also be recorded. Physical Therapy information will be gathered to test motor effect on lumbar epidurals.
- V. Opioid usage data will be recorded and converted to morphine equivalents and averaged for POD 0, 1, 2, and 3 per group.
- VI. Side effects such as pruritus, nausea/vomiting, and respiratory depression (defined as respiratory rate less than 10 breaths per minute of oxygen saturation more than 7 points lower that the patients preoperative value on room air) will be recorded and managed as deemed appropriate by the attending physician.
- VII. 24 hour I/O for the first 72 hours to assess fluid balance, length of stay, and amount of days before return to PO status.

Data analysis plan

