All data will be entered securely using the online database or Red Cap. To assess potential dose-response effects on changes in continuously measured primary outcomes, repeated measures mixed modeling analyses will be used. This type of analysis can assess the main effects of time (i.e., change) and group (i.e., epinephrine dose; coded as an ordinal variable) on the outcomes. Mixed models are the preferred approach to analyze data with repeated measures; these models can account for correlation among repeated measurements, flexible time effects, and can handle missing data. Additionally, this model can estimate time × group interactions. If this interaction is statistically significant, that provides evidence that the changes in outcomes are different depending on the dose of epinephrine that a patient received. Logistic regression models will be used to assess the relationship between epinephrine dose and incidence of hypotension (SBP < 20% or MAP < 55 mmHg) and other categorical outcome variables. A P value of <0.05 was considered statistically significant for all statistical tests. All analyses were conducted in JMP Pro 11.0 (SAS Institute, Cary, NC).

Sample size determination

At 80% power (alpha = 0.05), a sample of n=200 (50 per group) will be able to detect 26% differences in incidence of categorical outcomes, and an effect size of Cohen's f = 0.24 for group mean differences and effect size of Cohen's f = 0.09 for group differences mean change over time. Figure 1 depicts how these effect sizes will translate to the outcomes, with assumed standard deviations in outcomes ranging from 5 to 25. For example, assuming MAP has an SD = 10, the present study will be able to detect mean differences of 5 mmHg across groups and group differences of 3 mmHg for mean change over time.

ADMINISTRATIVE RESPONSIBILITIES:

Study Resources: The principal investigator will oversee the data collection, data analysis and will maintain the records in confidence. Should any evidence suggest that the study protocol require modification, the PI will notify the IRB in a timely manner for review and approval. Each subject will be identified by number, not by name, on all data forms. To protect confidentiality, all data will be numerically coded and information linking the numeric codes to individual participant's names will be kept in a locked file in the PI's office.

7. Possible Discomforts and Risks:

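### Hypotension incidence has no common observation window: ward blood pressure follow-up is tied to the epidural with no other stated end, and early stops and removals have no analysis rule

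*Combined protocol and SAP*

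**What the plan says.** In section 6, Primary measurements, Postoperative period II, ward readings of SBP, MAP and heart rate are taken every 4 to 6 hours, or hourly if there is concern, "for as long as the epidural analgesic blocks are continued, but at least every 8 hours after discharge from the PACU".

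The Secondary measurements list uses fixed periods instead. Block spread is tested "every 8 hours for the subsequent 72 hours after discharge from the PACU", opioid use is summarised for POD 0 to 3, ambulation for POD 1 to 3, and fluid balance for 72 hours.

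The schedule of activities in section 6 has two primary-measurement rows. One is for readings every 3 to 5 minutes. The other is "Primary measurements every 15 min" and is ticked up to 1 hour post-op. No row covers vital signs on the floor or on POD 1 to 3.

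The Data analysis plan states: "Logistic regression models will be used to assess the relationship between epinephrine dose and incidence of hypotension". It gives no time window, exposure adjustment or rule for patients whose infusion ends early. The definition of hypotension (Research-Related Procedures – Intraoperative) has no time frame either.

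The infusion can end early in three ways:

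- Section 7 turns it off for unwanted effects that could be attributed to epinephrine. No follow-up or removal rule is given.
- Research-Related Procedures - Preoperative Period treats a rate below the 4 to 8 mL per hour range as the end of need or as hypotension that cannot otherwise be treated. Again no follow-up rule is given.
- Research-Related Procedures – Intraoperative turns it down or off for significant hypotension, a fall in MAP or instability, and removes the patient from the study.

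**The concern.** Preventing hypotension is the title question. A yes/no incidence compares arms fairly only if every patient is observed over the same period, or if the analysis allows for different periods. Here the period may end with the infusion, and infusion length is a post-randomisation variable that treatment can affect. Stops for true epinephrine effects from the infusion can occur only in groups B and C, and might be more frequent at the higher concentration. A shorter window in those arms would lower their recorded hypotension, in the direction of the study hypothesis. End-of-need stops may also differ by arm if epinephrine changes analgesia, which is itself a study question; that direction is not predictable.

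Removal for low pressure acts differently. Such a patient has normally already met the event definition, so the risk is that the event leaves the analysis with the patient. An arm with more severe hypotension would lose more events.

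**Working it through.** **The plan's own figure.** Sample size determination says the trial "will be able to detect 26% differences in incidence of categorical outcomes" with 50 per group at 80% power and alpha 0.05. Sidedness and base rate are not stated. With a two-sided comparison of two proportions, 50 per group, 20% v 46% gives 79.9% power, so the figure reproduces at that base rate. At 37% v 63%, power is 74.6%. Neither result depends on length of follow-up, so they give scale only.

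**Inputs for the window effect.** The documents give no stopping rate, stopping time, base incidence or split of events between theatre and ward. All of the following are assumptions:

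- P: total incidence with full observation, 30%, the same in both arms (no true effect).
- a: the part of P occurring before the ward.
- Constant ward hazard over 72 hours, unchanged when the infusion stops.
- q: share stopped at 24 ward hours, not observed afterwards and kept in the model with no event recorded unless one came earlier.

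**Formulas.**

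- Recorded risk for a stopped patient: R = 1 − (1 − a) × [(1 − P)/(1 − a)]^(24/72)
- Spurious gap between arms: (q₂ − q₁) × (P − R)

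**Results for 30% v 0% stopped.**

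| Share of events before the ward | a | R | Gap |
|---|---|---|---|
| None | 0 | 1 − 0.70^(1/3) = 0.112 | 0.30 × (0.300 − 0.112) = 5.6 points |
| Half | 0.15 | 1 − 0.85 × (0.70/0.85)^(1/3) = 0.203 | 0.30 × (0.300 − 0.203) = 2.9 points |
| 80% | 0.24 | 1 − 0.76 × (0.70/0.76)^(1/3) = 0.261 | 0.30 × (0.300 − 0.261) = 1.2 points |

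**A milder contrast, 10% v 30% stopped, a = 0.** The gap is 0.20 × (P − R). Rejection rates are for a two-sided 5% test of two proportions, 50 per arm, with no true effect.

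| P | R | Gap | Rejection rate |
|---|---|---|---|
| 30% | 0.112 | 3.8 points | 7.1% |
| 50% | 0.206 | 5.9 points | 9.1% |
| 70% | 0.331 | 7.4 points | 11.8% |

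**Equal stopping still costs power.** With a = 0 and 30% of both arms stopped at 24 hours, a true 37% v 63% is recorded as 30.2% v 52.6%. Power at 50 per group falls from 74.6% to 62.6%.

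**Removal.** Suppose 15 of 50 patients in an arm have an event (30%). If one of them is removed and dropped from the analysis, incidence becomes 14/49 = 28.6%, a loss of 1.4 points per such patient. The plan does not say whether removed patients are dropped.

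**The case against.** The strongest reply is that the text does not say blood pressure ceases when the epidural does. The 8-hour minimum is anchored to PACU discharge and can be read as continuing after the block stops, much as block testing does at the same interval. That stands. A reader might infer that pressure is recorded only while the infusion runs, but this is one reading of an ambiguous sentence. What the sentence lacks on either reading is a stated end other than the epidural's.

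A reader might also infer that early-stopped patients are scored as event-free. No such rule is written. It is what a yes/no model does if a patient with no recorded event is kept, and the plan does not say whether such patients are kept.

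Stops for low pressure do not fit the short-window argument, because those patients have normally had an event and are removed. The window argument therefore rests on end-of-need stops and stops attributed to epinephrine, and no frequency is given for either.

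The schedule does not show that follow-up ends 1 hour post-op. Its two primary-measurement rows belong to the 3-to-5-minute and 15-minute frequencies, and pain scores and pain service records are ticked through POD 3. A ward vital-signs row is missing, which makes the table incomplete.

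The illustration is sensitive to its assumptions. Pressure is recorded most densely before and during surgery and in the PACU, periods that nearly all patients share, so the spurious gap may be small against the planned 26 points. If risk falls once the epidural is off, it is smaller still.

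Finally, hypotension while on the infusion is a defensible target, and the planned mixed models use the repeated readings. But an on-infusion target needs to be stated and analysed per unit of exposure, which the logistic model does not do.

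**Conclusion.** The point holds in limited form. Ward blood pressure has no clear end of follow-up, hypotension incidence has no common window, and early stops and removals have no analysis rule. The possible bias runs through stops attributed to epinephrine and end-of-need stops; removal for low pressure is a separate route by which events may be lost.

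The size cannot be known from the documents. At 30% total incidence with 30% v 0% stopping at 24 hours, the spurious gap runs from about 1.2 to 5.6 points, depending on how many events precede the ward. These figures assume equal true risk, constant ward hazard, no readings after the stop, and stopped patients kept in the model. The documents do not support the stronger claims that follow-up definitely ends with the epidural or that early stoppers are by rule counted as event-free. This is a sensible, inexpensive improvement and does not show that the planned comparison is invalid.

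**What to change.** - Record SBP, MAP and heart rate from routine ward vital signs to a fixed 72 hours after PACU discharge, or to hospital discharge if earlier, in every randomised patient given study drug, whether or not the infusion is running.
- Add a row for floor and POD 1 to 3 vital signs to the schedule of activities.
- Define hypotension incidence over that one window, starting with the study infusion, and count events up to and including any stop or removal.
- Record the infusion stop time and reason. Report events per hour on infusion as a sensitivity analysis.
- Reconcile the schedule, the removal wording, Primary measurements and the Data analysis plan, and say whether removal ends data collection or only study treatment.

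The clinical stopping rules are unchanged.

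The cost is a small amendment. The readings exist for inpatients, and the study already collects block, opioid and fluid data to 72 hours or POD 3. The main downside is that some off-infusion time enters the primary window, which the on-infusion analysis addresses. A few patients may leave hospital before 72 hours. Readings may also be less frequent after a stop, so a fixed window removes most, though not all, of the difference in detection.

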A limiting factor in the use of epidural analgesia, however, is the high incidence of associated hypotension. Hypotension is defined as systolic blood pressure (SBP) > 20% below the baseline preoperative measurements and acquired before the epidural or any sedation has been administered. Effective segmental epidural block would thus invariably cause sympathectomy due to its location in the thoracic or lumbar areas by blocking the cardiac sympathetic nerves, the pre-ganglionic nerves to the adrenal glands or the sympathetic nerves to the blood vessels individually or in combination.

It has been proven beyond doubt that epinephrine, when added to ropivacaine 0.2% and used for epidural analgesia by infusion, is safe and may even improve spinal cord blood flow and the analgesic effects of ropivacaine.⁷ It is also known that the cause of hypotension associated with epidural analgesia is the blockade of the sympathetic outflow to the cardiovascular and adrenal systems, and that the ideal mechanism to counter this would be by beta1-stimulation, which is ideally achieved with low-dose epinephrine.

Finally, it is known that epidural infused epinephrine increases its serum concentration.⁸ What is not known is whether added epinephrine will counteract this sympathetic blockade and prevent hypotension, and what the optimal concentration of epinephrine infusion would be during epidural analgesia with 0.2% ropivacaine to achieve optimal analgesia and optimal hemodynamic status.

5. Specific Aims:

We aim to examine whether adding epinephrine will counteract the sympathetic blockade and prevent hypotension, and what the optimal concentration of epinephrine infusion would be during epidural analgesia with 0.2% ropivacaine that can achieve both optimal analgesia and optimal hemodynamics. Specifically we plan to answer the following questions:

- 1. Does the addition of epinephrine to the epidural infusion of 0.2% ropivacaine:
 - a. Prevent hypotension?
 - b. Lead to a wider spread of local anesthetic effect?
 - c. Lead to a difference in the average pain scores?
 - d. Lead to a difference in when ambulation occurs?
 - e. Decrease potential of other opioid-related side effects such as pruritus, nausea/vomiting, respiratory depression and opioid consumption?
- 2. What is the optimal concentration of epinephrine (2mcg/mL or 5mcg/mL) to achieving the above-mentioned outcomes?

6. Research Plan:

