Up to 250 patients between the ages of 18 and 80 years undergoing epidural analgesia to treat perioperative pain associated with major surgery will be approached for their willingness to participate in the study. Patients undergoing major thoracic, abdominal, urological or orthopaedic surgery for whom thoracic or lumbar epidural block would be indicated and planned for intraoperative and postoperative analgesia as per the UF Acute Pain Service (APS) usual and routine practice will be included in this study. Our epidural failure rate is lower than 20% and our institution performs around 100 epidurals a month. If only a 1/3 of our patients agree to be part of our study we would have 24 study patients a month. This would then mean that our study would take 10 months to complete data collection.

Exclusion criteria:

Sepsis (febrile, above normal and upward trending white blood count, and/or positive cultures for systemic infection), patients with acute trauma, coagulopathy [INR >1.4, platelets < 100,000, and/or anticoagulation medication given out of UF APS adaptation of the American Society of Regional Anesthesiologists (ASRA) guidelines⁹, preoperative hemodynamic instability, symptomatic coronary artery disease (angina etc.), patients from the ICU whose tracheas were intubated for any cause, patient refusal, pregnancy, allergies to medications in the protocol, and primary or secondary block failure.

Standard of Care - Preoperative Period:

All patients will receive a standardized continuous epidural block at the appropriate level for the planned surgery by the APS physician staffing the block room that day. For the standardized continuous epidural block, placement will be confirmed with loss of resistance technique (LORA), wave form analysis or nerve stimulation.

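### Pre-operative opioid dose is neither specified for capture nor used in the analysis, so the raw per-group opioid averages for Aim 1e may be imprecise

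*Combined protocol and SAP*

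**What the plan says.** - **Aim (5. Specific Aims, 1e).** The trial asks whether epinephrine will "Decrease potential of other opioid-related side effects such as pruritus, nausea/vomiting, respiratory depression and opioid consumption".
- **Eligibility (6. Research Plan, Inclusion and Exclusion criteria).** The population is "Patients undergoing major thoracic, abdominal, urological or orthopaedic surgery for whom thoracic or lumbar epidural block would be indicated", aged 18 to 80. Patients need not be opioid-naive. The exclusion list, which ends with "patient refusal, pregnancy, allergies to medications in the protocol, and primary or secondary block failure", does not mention chronic opioid use, tolerance or chronic pain.
- **Data capture (activity schedule in 6. Research Plan).** The row "Record opioid usage" is marked for the PACU, one hour post-op, transfer to the floor and POD 1 to 3. It is blank for screening, every pre-op column and the intra-op column. "Medical History" is marked at screening, but its content is not specified and no analysis refers to it.
- **Summary (Secondary measurements, item V).** "Opioid usage data will be recorded and converted to morphine equivalents and averaged for POD 0, 1, 2, and 3 per group".
- **Model (Data analysis plan).** "To assess potential dose-response effects on changes in continuously measured primary outcomes, repeated measures mixed modeling analyses will be used". Logistic regression is for hypotension and other categorical outcomes. Opioid consumption is continuous and secondary, so neither statement covers it. No covariate, transformation or robust summary is given for it.
- **Allocation (Research-Related Procedures, Preoperative Period).** Randomization is computer-generated, with no stratification factor stated.

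**The concern.** A patient on long-term opioids may use much more after surgery than an opioid-naive patient, for reasons unrelated to the epidural solution. If such patients are enrolled and their pre-operative dose is not in the data set, the spread they add stays in the error term. The arm means then also depend on how many of them fall in each arm by chance. The raw mean is the summary most exposed to this.

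At stake is the precision of one secondary comparison. It has some further reach, because Aim 2 judges the epinephrine concentration on the outcomes listed under Aim 1, and opioid consumption is among them.

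**Working it through.** **The plan's own figure.** There is none for this outcome. Sample size determination gives no mean or SD for morphine equivalents. Its general figure for group means (Cohen's f = 0.24 with 200 patients in four groups) reproduces: one-way ANOVA gives f = 0.236 at 80% power. It does not depend on this point.

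**Inputs.** From the documents: 50 patients per group. Assumed, because the documents are silent: opioid-naive mean 30 and SD 20 morphine equivalents per day; a fraction f of patients is tolerant; tolerant patients have k times both the mean and the SD.

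**Variance with and without adjustment for tolerance.**
- Within classes (left after adjustment): W = (1−f)·20² + f·(20k)²
- Between classes (removed by adjustment): B = f(1−f)·(30k−30)²
- Ratio of unadjusted to adjusted variance: (W+B)/W

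For f = 0.2 and k = 3:
- W = 0.8·400 + 0.2·3600 = 1040 (SD 32.2)
- B = 0.16·3600 = 576
- Total = 1616 (SD 40.2), so the ratio is 1616/1040 = 1.55. The unadjusted comparison needs 1.55 times the patients for the same precision.
- Share of variance removed by adjustment: 576/1616 = 36%
- Tolerant patients' share of all opioid: 0.2·90/(0.2·90 + 0.8·30) = 18/42 = 43%

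The same formula elsewhere gives these ratios:

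| Tolerant share | k = 2 | k = 3 | k = 4 |
|---|---|---|---|
| 2% | 1.04 | 1.15 | 1.31 |
| 5% | 1.09 | 1.31 | 1.55 |
| 10% | 1.16 | 1.45 | 1.73 |
| 20% | 1.23 | 1.55 | 1.81 |
| 30% | 1.25 | 1.56 | 1.77 |

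Over 10–30% and k = 2–4 the range is 1.16 (520 + 81 = 601; 601/520) to 1.81 (1600 + 1296 = 2896; 2896/1600). Adjustment removes at most 1296/2896 = 45% of the variance in that range.

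**Power, on a second set of assumptions.** Within-class coefficient of variation 0.6, a true 30% reduction in every patient (SD reduced in proportion), 50 per arm, two-sided alpha 0.05. For 10% tolerant and k = 3, in units of the naive mean:
- Control mean 0.9 + 0.1·3 = 1.2; effect 0.3·1.2 = 0.36
- Control W = 0.36·(0.9 + 0.1·9) = 0.648; B = 0.09·2² = 0.36; total 1.008
- Treated-arm variances are 0.7² = 0.49 times these, so the two-arm average is 0.745 times the control value: 0.751 raw, 0.483 adjusted
- z = 0.36/√(2·0.751/50) = 2.08 raw; 0.36/√(2·0.483/50) = 2.59 adjusted
- Power: Φ(2.08 − 1.96) = 55% raw; Φ(2.59 − 1.96) = 74% adjusted

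The same calculation gives 63% raw and 77% adjusted at 5% and k = 3, and 80% and 82% at 2% and k = 2. With no tolerant patients it is 83%.

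**Chance imbalance.** With 50 per arm, two arms differ by three or more tolerant patients with probability 24% at 5% prevalence and 40% at 10%. With naive mean 30 and k = 3, such a difference of three shifts the contrast in raw means by (3/50)·(90−30) = 3.6 per day. At 10% prevalence the overall mean is 0.9·30 + 0.1·90 = 36, so a 30% reduction is 10.8. The shift is one third of that.

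**The case against.** The strongest reply is that nothing in the documents says tolerant patients will be numerous or will consume several times as much. A reader might infer that a few such patients determine the opioid result. That is not supported. Prevalence and consumption ratio are both unstated, and 20% of 50 is ten patients per arm, not a few. Across 10–30% and k = 2–4, adjustment removes less than half the variance everywhere.

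Other parts of the reply also stand:
- Allocation is randomized, so no arm is systematically favoured.
- Pre-operative use may be recoverable. A medical history is taken at screening and Acute Pain Service records are collected from the pre-op period. The documents do not show that the dose goes unrecorded, only that its capture and use are not specified.
- The documents do not say whether home opioids are continued or counted, so counting of maintenance doses is an inference.
- The variance ratios assume adjustment for a perfectly known yes/no class on the raw scale. The gain from a rank or log analysis adjusted for dose was not computed.

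A reader might also extend the point to pain scores and opioid side effects. No calculation supports that. Pain is among the primary measurements, for which pre-operative readings and a repeated-measures model are planned. The saturation criterion for respiratory depression is already relative to the patient's own pre-operative value.

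The reply leaves the gap itself in place: an outcome named in an aim has a raw average as its only summary, with no stated test or covariate.

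**Conclusion.** The point holds as an optional improvement to one secondary outcome. Chronic opioid users are eligible, capture of pre-operative dose is not specified, and the only stated summary is a raw mean per group. The consequence is possible loss of precision and sensitivity to chance imbalance, not bias.

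The size rests on assumed values. The unadjusted variance is 1.16–1.81 times the adjusted variance for 10–30% tolerant patients at 2–4 times the consumption (naive mean 30, SD 20). The loss is negligible where tolerant patients are rare and consume only moderately more (1.04 at 2% and twice the consumption). Rarity alone does not remove it if the consumption ratio is high (1.31 at 2% and four times), although 2% is only one patient per arm on average. The planned sample size is unaffected.

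**What to change.** 1. Specify that the screening medical history records the pre-operative daily opioid dose, converted to morphine equivalents, with zero entered for non-users.
2. In item V and the Data analysis plan, replace the raw per-group averages for POD 0 to 3 with a pre-specified between-group comparison of morphine equivalents, adjusted for that dose. A rank-based analysis, such as analysis of covariance on ranks, is the simpler choice. A log scale also works, but needs a stated rule for zero consumption, which is plausible because the postoperative section offers opioids only as needed. Raw means can stay as description.

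The cost is one case-report field with a dose conversion, one covariate, and an adjusted estimate that is slightly harder to explain than a mean. Nobody is excluded, and treatment and sample size do not change.
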